### 3.2.2. Dose Levels and Cohorts

The Dose Escalation part of the study will begin the following planned dose levels and cohorts:

- **Dose Level 1:** 2 mg/kg biweekly\*\*
- **Dose Level 2:** 2.5 mg/kg\* weekly\*\*
- **Dose Level 3:** 4.5 mg/kg weekly\*\*
- **Dose Level 4:** 10 mg/kg weekly\*\*
- **Dose Level 5:** 20 mg/kg weekly\*\*
- **Dose Level 6:** 30 mg/kg weekly\*\*

\*\* Cohort 1: Biweekly (Q2W) for Cycles 1 through 6 followed by every 4 weeks (Q4W) thereafter. Cohort 2 and above: Weekly (QW) dosing for Cycles 1 and 2. Subjects may continue QW dosing until overall response (e.g., CR, CRh, or CRi) is achieved, at which time they may switch to Q2W dosing.

The planned dose levels for Dose Escalation include a maximum dose increment of less than a half-log (233%) between each dose level. Using the Escalation/De-escalation Rules governed by the BON design, if criteria is met allowing dose escalation, the subsequent dose level will first be evaluated against the Dose Increment Modification Rules For Dose Escalation ([Table 2](#)) taking into consideration the number of adverse events (Grade  $\geq 2$ ) and dose limiting toxicities which occurred at the current dose level prior to selecting the next dose.

In the event a dose increment modification is indicated during the Dose Escalation phase of the study, an ad-hoc safety meeting will occur with the Clinical Study Team to review the adverse event(s) against the qualifying criteria before any dose modifications are made.

All Adverse Events (excluding AEs unequivocally due to the underlying disease or an extraneous cause) occurring during the DLT Observation Period will be evaluated against the Dose Increment Modification rules, as follows:

- Limit the maximum dose increment to 100% if patients of a given cohort experience one Grade  $\geq 2$  AE (except for AEs unequivocally due to the underlying disease or an extraneous cause) during the DLT period.
  - *Example: If one  $\geq$  Grade 2 AE occurs in Dose Cohort 1 (2mg/kg), the subsequent dose level will be increased by 100% (4mg/kg) instead of the originally planned dose of 4.5mg/kg.*

- Limit the maximum dose increment to 50% if patients of a given cohort experience two or more Grade  $\geq 2$  AEs (except for AEs unequivocally due to the underlying disease or an extraneous cause) during the DLT period.
  - *Example: If two or more  $\geq$  Grade 2 AE occurs in Dose Cohort 1 (2mg/kg), the subsequent dose level will be increased by 50% (3mg/kg) instead of the originally planned dose of 4.5mg/kg.*
- Limit the maximum dose increment to 50% if patients of a given cohort experience one DLT during the DLT period.
  - *Example: If one DLT occurs in Dose Cohort 1 (2mg/kg), the subsequent dose level will be increased by 50% (3mg/kg) instead of the originally planned dose of 4.5mg/kg.*
- Limit the maximum dose increment to 30% if patients of a given cohort experience two DLTs during the DLT period.
  - *Example: If two DLTs occur in Dose Cohort 1 (2mg/kg), the subsequent dose level will be increased by 30% (2.6mg/kg) instead of the originally planned dose of 4.5mg/kg.*

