### Dose Levels and Cohorts

The Dose Escalation part of the study will begin with the following planned dose levels and cohorts:

- **Dose Level 1:** 2 mg/kg biweekly\*
- **Dose Level 2:** 2.5 mg/kg weekly\*
- **Dose Level 3:** 4.5 mg/kg weekly\*
- **Dose Level 4:** 10 mg/kg weekly\*
- **Dose Level 5:** 20 mg/kg weekly\*
- **Dose Level 6:** 30 mg/kg weekly\*

\*Cohort 1: Biweekly (Q2W) for Cycles 1 through 6 followed by every 4 weeks (Q4W) thereafter. For Cohort 2 and Above: Weekly (QW) dosing for Cycles 1 and 2. Subjects may continue weekly (QW) dosing until overall response (e.g., CR, CRh, or CRI) is achieved, at which time they may switch to biweekly (Q2W) dosing. For subjects who maintain a weekly dosing schedule, local bone marrow biopsies and aspirates should continue to be collected every 28-days.

The planned dose levels for Dose Escalation include a maximum dose increment of less than a half-log (233%) between each dose level. Using the Escalation/De-escalation Rules governed by the BON design, if criteria is met allowing dose escalation, the subsequent dose level will first be evaluated against the Dose Increment Modification Rules For Dose Escalation ([Table S2](#)) taking into consideration the number of adverse events (Grade  $\geq 2$ ) and dose limiting toxicities which occurred at the current dose level prior to selecting the next dose.

In the event a dose increment modification is indicated during the Dose Escalation phase of the study, an ad-hoc safety meeting will occur with the Clinical Study Team to review the adverse event(s) against the qualifying criteria before any dose modifications are made.

All Adverse Events (excluding AEs unequivocally due to the underlying disease or an extraneous cause) occurring during the DLT Observation Period will be evaluated against the Dose Increment Modification rules, as follows:

- Limit the maximum dose increment to 100% if patients of a given cohort experience one Grade  $\geq 2$  AE during the DLT period.
  - *Example: If one  $\geq$  Grade 2 AE occurs in Dose Cohort 1 (2mg/kg), the subsequent dose level will be increased by 100% (4mg/kg) instead of the originally planned dose of 4.5mg/kg.*
- Limit the maximum dose increment to 50% if patients of a given cohort experience two or more Grade  $\geq 2$  AEs during the DLT period.

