  - *Example: If two or more  $\geq$  Grade 2 AE occurs in Dose Cohort 1 (2mg/kg), the subsequent dose level will be increased by 50% (3mg/kg) instead of the originally planned dose of 4.5mg/kg.*
- Limit the maximum dose increment to 50% if patients of a given cohort experience one DLT during the DLT period.
  - *Example: If one DLT occurs in Dose Cohort 1 (2mg/kg), the subsequent dose level will be increased by 50% (3mg/kg) instead of the originally planned dose of 4.5mg/kg.*
- Limit the maximum dose increment to 30% if patients of a given cohort experience two DLTs during the DLT period.
  - *Example: If two DLTs occur in Dose Cohort 1 (2mg/kg), the subsequent dose level will be increased by 30% (2.6mg/kg) instead of the originally planned dose of 4.5mg/kg.*

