**Table 2: Dose Increment Modification Rules for Dose Escalation**

Dose Cohort	Planned Dose (mg/kg)	Frequency*	Dose Increment Modification During DLT Observation Period				
			If No DLT and/or no Grade $\geq 2$ AE a in a given cohort	If one Grade $\geq 2$ AE a in a given cohort	If two or more Grade $\geq 2$ AEs a in a given cohort	If One DLT in a given cohort	If 2 DLTs in a given cohort
1	2	Q2W	Dose increment as planned	Maximum dose increment to 100%	Maximum dose increment to 50%	Maximum dose increment to 30%	
2	2.5	QW					
3	4.5	QW					
4	10	QW					
5	20	QW					
6	30	QW					

a Adverse events (except for AEs unequivocally due to the underlying disease or an extraneous cause) occurring during the DLT Observation Period will be evaluated against the Dose Increment Modification rule.

\*Cohort 1: Biweekly (Q2W) for Cycles 1 through 6 followed by every 4 weeks (Q4W) thereafter. Cohort 2 and above: QW dosing for Cycles 1 and 2. Subjects may continue QW dosing until overall response (e.g., CR, CRh, or CRI) is achieved, at which time they may switch to Q2W dosing.

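### The worked examples of the dose-increment caps assume that 4.5 mg/kg follows Cohort 1; against the current 2.5 mg/kg level they give a higher dose after toxicity than after none

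*Combined protocol and SAP*

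**What the plan says.** The current ladder has six levels. The synopsis and Section 3.2.2 list 2 mg/kg every two weeks, then "2.5 mg/kg weekly", then 4.5, 10, 20 and 30 mg/kg weekly. Tables S2 and 2 give the same ladder, and Appendix 7 has the same order of doses.

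Once Table 1 allows escalation, the next dose is checked against the increment rules. With no toxicity, Table 2 says "Dose increment as planned", which from Cohort 1 means 2.5 mg/kg. With toxicity, the rules set ceilings: 100% after one Grade 2 or higher adverse event, 50% after two or more such events, 50% after one DLT, and 30% after two DLTs. The last reads "Limit the maximum dose increment to 30% if patients of a given cohort experience two DLTs during the DLT period".

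Each ceiling has a worked example starting from Cohort 1, printed in both the synopsis and Section 3.2.2. For one adverse event: "the subsequent dose level will be increased by 100% (4mg/kg) instead of the originally planned dose of 4.5mg/kg". For two or more events, and again for one DLT: "the subsequent dose level will be increased by 50% (3mg/kg) instead of the originally planned dose of 4.5mg/kg". For two DLTs the figure is 2.6 mg/kg, also set against 4.5 mg/kg.

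Section 1.2.1 still prints a five-level ladder in which Dose Level 2 is 4.5 mg/kg.

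**The concern.** The examples and the dose list in the same subsection disagree about which dose follows Cohort 1. The examples also state the ceiling as the dose that will be given. Under a ladder whose next level is 4.5 mg/kg, that is a reduction. Under the current ladder, whose next level is 2.5 mg/kg, it is an increase.

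The caps exist to slow escalation when toxicity appears. Read as written, the only illustrations of how to apply them do the reverse at the first step of a first-in-human trial. The situation can arise easily. Under the accelerated titration in Section 10.2.1, step 1, a single Grade 2 toxicity in the first subject does not hold the dose: the next subjects go to Dose Level 2, which is 2.5 mg/kg. The example for the same event says 4 mg/kg.

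**Working it through.** **Inputs.** Cohort 1 dose 2 mg/kg; current Dose Level 2, 2.5 mg/kg (synopsis, Section 3.2.2, Table 2); Dose Level 2 in Section 1.2.1, 4.5 mg/kg; caps 100%, 50%, 50% and 30% (Section 3.2.2).

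**Formulas.** Capped dose = current dose × (1 + cap). Under a rule that limits the maximum increment, next dose = the lower of planned dose and capped dose.

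**Step 1: reproduce the plan's figures.** 2 × 2.0 = 4.0; 2 × 1.5 = 3.0 (twice); 2 × 1.3 = 2.6 mg/kg. All four example doses reproduce exactly.

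**Step 2: find the ladder they fit.** In Section 1.2.1 the step from 2 to 4.5 mg/kg is 4.5/2 − 1 = +125%. Every cap binds, and the lower of 4.5 and the capped dose is 4, 3, 3 and 2.6. The examples are therefore consistent with the five-level ladder. In the current ladder the step is 2.5/2 − 1 = +25%, below every cap, so none binds.

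**Step 3: compare under the current ladder (mg/kg per infusion).**

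| Event in Cohort 1 | Example dose | Rule: lower of 2.5 and capped dose | Example over 2.5 |
|---|---|---|---|
| One Grade 2+ AE | 4 | 2.5 | 4/2.5 = 1.60, +60% |
| Two or more Grade 2+ AEs | 3 | 2.5 | 3/2.5 = 1.20, +20% |
| One DLT | 3 | 2.5 | 3/2.5 = 1.20, +20% |
| Two DLTs | 2.6 | 2.5 | 2.6/2.5 = 1.04, +4% |

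The excesses are 1.5, 0.5, 0.5 and 0.1 mg/kg. Cohort 2 and above are dosed weekly, so an example dose and 2.5 mg/kg would be given on the same schedule.

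**Step 4: see which rows can occur.** Table 1 must first allow escalation.
- One Grade 2+ AE: reachable with the first subject (Section 10.2.1, step 1).
- Two or more Grade 2+ AEs and no DLT: reachable with 3 evaluable subjects, where Table 1 escalates on 0 DLTs.
- One DLT: Table 1 escalates only from 6 evaluable subjects.
- Two DLTs: Table 1 escalates only from 11. Section 10.2.1 limits a cohort to 12, and it stops escalation at 9 evaluable subjects if the decision is to stay, which is the decision for 2 DLTs in 9. This row is close to unreachable.

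**Step 5: find a step that illustrates the caps.** The increments of the current ladder are +25%, +80%, +122%, +100% and +50%. Only 4.5 to 10 mg/kg (10/4.5 − 1 = +122%) exceeds all the caps. There the capped doses are 4.5 × 2.0 = 9.0, 4.5 × 1.5 = 6.75 (twice) and 4.5 × 1.3 = 5.85 mg/kg, all below 10.

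**The case against.** The best defence is that the rule is right and only the illustrations are out of date. Each rule, and Table 2, speaks of a maximum. A maximum applied to a planned +25% step leaves 2.5 mg/kg, so a team that follows the rule makes no error. In addition, before any modification "an ad-hoc safety meeting will occur with the Clinical Study Team", Section 9.5 has increment modifications evaluated at the dose escalation meetings, and the tables show 2.5 mg/kg. Even the largest example, 4 mg/kg, lies below Dose Level 3 (4.5 mg/kg weekly) and far below the human-equivalent NOAEL of 85 mg/kg in Section 1.2.1.

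Most of this stands, and it limits the consequence. It does not make the examples harmless. They are forward-looking, and Cohort 1 is still the first row of Table 2, so they cannot be read as history. No sentence says that the lower of planned and capped applies, and the meeting would judge events against criteria that have these examples directly beneath them.

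Three stronger readings do not hold:
- A reader might infer that the caps apply to cumulative dose, since this step also moves from two-weekly to weekly dosing, and that the planned step itself breaches them. Table 2 lists mg/kg apart from frequency, every example takes its percentage on mg/kg per dose, and nowhere is an increment expressed per cycle. One clarifying phrase is enough.
- A reader might infer that the caps allow escalation after DLTs that Table 1 would not. Section 3.2.2 applies them only "if criteria is met allowing dose escalation", and Section 10.2.1, step 2, says the same. That condition needs no restating.
- A reader might count the mismatch with Section 10.2.1, step 1, as a second defect. It is the same 4.5 mg/kg premise seen from another section.

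**Conclusion.** The inconsistency is real and should be corrected. All four examples, in two places, rest on a next dose of 4.5 mg/kg that the current ladder does not have. Read literally, they raise the dose after Cohort 1 by 60%, 20%, 20% or 4% over the dose planned after no toxicity. The rule, as distinct from its examples, gives 2.5 mg/kg in every case.

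This rests on two readings that the documents support: increments are in mg/kg per infusion, and Cohort 2 is dosed weekly whatever its dose. The exposure that matters is the two adverse-event rows; the DLT rows need at least 6 or 11 evaluable subjects at Dose Level 1. Only this step is affected, and a safety review stands in front of it. Severity is low to moderate. It should still be fixed, because these are wrong dose figures inside an operative escalation rule. Confidence is high.

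**What to change.** In the synopsis and Section 3.2.2, replace the four examples with the step from 4.5 to 10 mg/kg:
- 9.0 mg/kg after one Grade 2 or higher adverse event;
- 6.75 mg/kg after two or more such events, or after one DLT;
- 5.85 mg/kg after two DLTs.

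Add one sentence: the next dose is the lower of the planned dose and the capped dose, with increments measured in mg/kg per infusion. Update the ladder in Section 1.2.1 to the six current levels.

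The cost is wording only. The cap percentages, the Table 1 boundaries and the number of subjects stay as they are.

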**Table 2: Dose Increment Modification Rules for Dose Escalation**

Dose Cohort	Planned Dose (mg/kg)	Frequency*	Dose Increment Modification During DLT Observation Period				
			If No DLT and/or no Grade $\geq 2$ AE a in a given cohort	If one Grade $\geq 2$ AE a in a given cohort	If two or more Grade $\geq 2$ AEs a in a given cohort	If One DLT in a given cohort	If 2 DLTs in a given cohort
1	2	Q2W	Dose increment as planned	Maximum dose increment to 100%	Maximum dose increment to 50%	Maximum dose increment to 30%	
2	2.5	QW					
3	4.5	QW					
4	10	QW					
5	20	QW					
6	30	QW					

a Adverse events (except for AEs unequivocally due to the underlying disease or an extraneous cause) occurring during the DLT Observation Period will be evaluated against the Dose Increment Modification rule.

\*Cohort 1: Biweekly (Q2W) for Cycles 1 through 6 followed by every 4 weeks (Q4W) thereafter. Cohort 2 and above: QW dosing for Cycles 1 and 2. Subjects may continue QW dosing until overall response (e.g., CR, CRh, or CRI) is achieved, at which time they may switch to Q2W dosing.

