The effectiveness results from CDX murine models were integrated to calculate the doses that lead to 30% (PD30 0.72 mg/kg), 50% (PD50 1.7 mg/kg) and 90% (PD90 15.3 mg/kg) of the maximum effect. Serum concentrations in mice were fit to a PK model, which was used to simulate the exposures in mice after multiple dosing. Simulations of 6 doses administered once weekly in 20 gram (healthy) mice were performed to predict the exposures in CDX murine models under the assumption of equivalence in PK with healthy mice. The median simulated trough concentrations (minimum concentration at the end of the dosing interval) at the 3 dose levels were used to approximate efficacy thresholds.

Single species allometric scaling was used to derive human pharmacokinetic parameters from Cynomolgus monkeys' pharmacokinetics. The human PK model was used to simulate serum concentrations at different doses administered every two weeks, and the 95% CI of the simulated human trough values were compared to the simulated efficacy thresholds in mice. The comparison led to the conclusion that 2 mg/kg every two weeks in humans would lead to the majority of subjects with trough levels slightly above the median CDX mouse PD30 trough levels and a 5 mg/kg dose would lead to the majority of subjects with a trough levels above the determined PD50. A dose of 30 mg/kg is predicted to result trough levels comparable to the PD90 identified from the CDX murine model.

Therefore, the proposed planned dosing rationale is summarized, incorporating dose increment to less than a half-log (233%) between each dose level, as follows:

- Dose Level 1: 2 mg/kg as an approximation of the minimally active dose (PD30)
- Dose Level 2: 4.5 mg/kg as an approximation of PD50
- Dose Level 3: 10 mg/kg to support the characterization of the dose effect curve

- Dose Level 4: 20 mg/kg to support the characterization of the dose effect curve
- Dose Level 5: 30 mg/kg as an approximation of PD90

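### The four worked examples of the dose-increment rule use an outdated planned dose of 4.5 mg/kg after Cohort 1, and the and/or heading in Tables 2 and S2 needs a wording correction

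*Combined protocol and SAP*

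**What the plan says.** Once the BOIN rule allows escalation, the next dose is checked against the dose-increment rule (section 3.2.2 and Table 2; synopsis and Table S2; section 10.2.1, step 2, also points to Table 2). The bullets set maximum increments of 100% after one Grade ≥2 AE, 50% after two or more, 50% after one DLT and 30% after two DLTs. The first reads "Limit the maximum dose increment to 100% if patients of a given cohort experience one Grade" ≥2 AE in the DLT period. None of the AE bullets requires a DLT.

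Each bullet carries an example starting from Cohort 1:

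- One Grade ≥2 AE: "the subsequent dose level will be increased by 100% (4mg/kg) instead of the originally planned dose of 4.5mg/kg".
- Two or more Grade ≥2 AEs, and separately one DLT: "the subsequent dose level will be increased by 50% (3mg/kg) instead of the originally planned dose of 4.5mg/kg".
- Two DLTs: "the subsequent dose level will be increased by 30% (2.6mg/kg) instead of the originally planned dose of 4.5mg/kg".

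The dose lists in 3.2.2 and the synopsis, Tables 2 and S2, and Appendix 7 all place 2.5 mg/kg between 2 and 4.5 mg/kg; the synopsis gives Dose Level 2 as "2.5 mg/kg weekly". Section 1.2.1 still prints a five-level list with "Dose Level 2: 4.5 mg/kg as an approximation of PD50".

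In both tables, the column that gives the full planned step is headed "If No DLT and/or no Grade" ≥2 AE. Section 3.2.2 adds: "In the event a dose increment modification is indicated during the Dose Escalation phase of the study, an ad-hoc safety meeting will occur".

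**The concern.** The rule sets the ceiling on the next dose in a first-in-human trial, and the examples are its only illustration. They are meant to show toxicity holding the dose back. Set against the current dose list, each shows a dose higher than a cohort without toxicity would receive, and says that the dose will be increased to that level. None shows a step at which a cap lowers a dose now planned.

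The table heading is a smaller matter. With *and/or*, a cohort with no DLT but with Grade ≥2 AEs satisfies the uncapped column and a capped column together. A reader using the table alone would find two answers.

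**Working it through.** **Inputs.** Planned doses are 2 (Q2W), then 2.5, 4.5, 10, 20 and 30 mg/kg (QW), from 3.2.2 and Table 2. Caps are 100%, 50%, 50% and 30%, from the bullets in 3.2.2.

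**Reproducing the plan's figures.** Capped dose = current dose × (1 + cap). From 2 mg/kg: 2 × 2.0 = 4; 2 × 1.5 = 3 (twice); 2 × 1.3 = 2.6. The arithmetic is right, and it works on mg/kg per infusion.

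**Checking the comparator.** The examples compare with 4.5 mg/kg, an increment of 4.5/2 − 1 = 125%. The dose now planned after Cohort 1 is 2.5 mg/kg, an increment of 2.5/2 − 1 = 25%. Against 2.5 mg/kg the illustrated doses are 4/2.5 = 1.60, 3/2.5 = 1.20 (twice) and 2.6/2.5 = 1.04. Since 25% is below every cap, the lower of planned and capped dose is 2.5 mg/kg in all four cases. Replacing 4.5 by 2.5 in the examples would therefore not repair them, because no cap would bind.

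**All steps, per infusion (mg/kg).**

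| Step | Planned increment | 100% cap | 50% cap | 30% cap |
|---|---|---|---|---|
| 2 to 2.5 | 25% | 4 | 3 | 2.6 |
| 2.5 to 4.5 | 80% | 5 | 3.75 | 3.25 |
| 4.5 to 10 | 122% | 9 | 6.75 | 5.85 |
| 10 to 20 | 100% | 20 | 15 | 13 |
| 20 to 30 | 50% | 40 | 30 | 26 |

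The step from 4.5 to 10 mg/kg is the only one at which every cap falls below the planned dose.

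**Which examples can arise.** By the escalation row of Table 1, escalating with one DLT needs at least 6 evaluable subjects and with two DLTs at least 11. The two Grade ≥2 AE examples are the practical ones. Under the accelerated titration in 10.2.1, a single Cohort 1 subject with one Grade 2 AE and no DLT could lead straight to escalation.

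**Heading.** Under *or*, a cohort with 0 DLTs always qualifies for the full planned step. It would also fall in the 100% column with one Grade ≥2 AE, or in the 50% column with two or more. Under *and*, the uncapped column holds only cohorts with 0 DLTs and 0 Grade ≥2 AEs, and the overlap disappears. If the heading were followed against the bullets:

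- One Grade ≥2 AE: the dose would differ only at 4.5 to 10 mg/kg (10 v 9; 10/9 = 1.11).
- Two or more: it would differ at 2.5 to 4.5 (4.5/3.75 = 1.20), 4.5 to 10 (10/6.75 = 1.48) and 10 to 20 (20/15 = 1.33).

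**Scale.** The rule does not say whether increments are per infusion or per week. This matters at one step. Going from 2 mg/kg Q2W (2/2 = 1 mg/kg per week) to 2.5 mg/kg QW is +25% per infusion but 2.5/1 − 1 = +150% per week. On a weekly scale the caps would be 2, 1.5 and 1.3 mg/kg per week, and all would bind.

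**The case against.** The strongest reply is that the examples are not the rule. Each sits under a bullet that limits a maximum increment, and a maximum cannot raise a planned dose. Each also presents its dose as a reduction from 4.5 mg/kg. This stands. A reader might infer that the plan prescribes a higher dose after toxicity; the bullets do not support that.

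A reader might also infer from the heading that a cohort with Grade ≥2 AEs and no DLT may take the full step. The documents do not support this either. The bullets cap such a cohort without condition. Under *or*, the two AE columns would apply only where a DLT is also present, and there the DLT columns already give a cap at least as strict, so they would have no work to do. Nor does an escalation go ahead on the heading alone: 3.2.2 and step 2 of 10.2.1 require the increment check whenever escalation criteria are met, and the team conferences in section 9.5 evaluate increment modifications. The ad-hoc meeting is weaker support, since it is held only once a modification is indicated.

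Finally, Cohort 1 may be closed. Table 7 shows only weekly dosing in Cycles 1 and 2, which hints at this, but the documents do not say so. If it is closed, the examples affect no further step from 2 mg/kg. They would still be the only illustration for later cohorts.

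**Conclusion.** The error in the examples is confirmed. All four, in both places, use a planned dose that belongs to the five-level list in 1.2.1. The illustrated doses exceed the current planned 2.5 mg/kg by 60%, 20%, 20% and 4%. This is a wrong figure inside an operative dose rule and should be corrected, although the intended rule can be recovered from the bullets.

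The heading is a real but secondary wording error. The gaps of 11% to 48% describe only what would follow if it were read against the bullets; they are not an expected effect of the plan.

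The step-by-step figures assume increments per infusion, which the examples' arithmetic implies and the plan does not state. The percentages against 2.5 mg/kg compare single infusions. Nothing in the documents shows that any subject received a dose set from these examples.

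**What to change.** 1. In 3.2.2 and the synopsis, replace the four examples with ones from Cohort 3 (4.5 mg/kg QW, planned next dose 10 mg/kg): at most 4.5 × 2.0 = 9 mg/kg after one Grade ≥2 AE; 4.5 × 1.5 = 6.75 mg/kg after two or more; 6.75 mg/kg after one DLT; 4.5 × 1.3 = 5.85 mg/kg after two DLTs.
2. In Tables 2 and S2, change the first column heading to *If no DLT and no Grade ≥2 AE in a given cohort*.
3. Add to the rule: *The next dose is the lower of the planned dose and the capped dose, with increments calculated per infusion in mg/kg.* The sponsor should confirm the per-infusion scale, in particular for the change from Q2W to QW.

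The cost is wording only: four examples in two places, one heading in two tables and one added sentence. Sample size, visits and the BOIN boundaries do not change.
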